- Subjects who reported greater than 10 days (aggregate total) of concomitant NSAID use (any dosage of NSAIDs, for conditions other than OA) in a SC dosing interval (defined as the period of 8 weeks between 2 SC doses) and who after counseling report further concomitant NSAID use should be withdrawn from investigational product and entered in the Early Termination Follow-Up period (refer to Section 6.4).

Subjects will be instructed that many over-the-counter medications contain NSAIDs and to be aware of this during their selection of OTC medications.

Herbal, homeopathic, and naturopathic remedies should not be initiated during the study; however, subjects who have taken a stable dose of these products for at least 30 days prior to the IPAP will be allowed to continue their regimen. Subjects should be advised that St. John's Wort and other inducers of the cytochrome (CYP3A4/5) enzyme system (eg, carbamazepine and rifampin) may interfere with the efficacy of hormonal contraceptive products.

Biologics (for example: TNF- $\alpha$  inhibitors such as adalimumab, etanercept, infliximab) other than investigational product, and live attenuated vaccines must not have been taken within 3 months prior to the IPAP and are prohibited during the study. Flumist® Influenza Virus Vaccine Live, Intranasal or other inhaled influenza vaccines (in regions where these vaccines are approved) are the only exception of a live attenuated vaccine that will be permitted during the study.

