#### 5.8.2. Permitted Medications

Daily low dose aspirin ( $\leq$ 325 mg or per local prescribing practice) therapy for cardiovascular prophylaxis is permitted without restriction.

Medications for other (non-osteoarthritis, non-pain) conditions are permitted provided the subject has received a stable dose for at least 30 days before the IPAP (30 days prior to Screening for antihypertensive medications) and the dose is not expected to change during the study. Note however that dose adjustments (includes starting a new therapy) during the study can be made if required, and recorded on the concomitant medication CRF.

Occasional use of pain medications for pain is permitted in situations such as outpatient diagnostic procedures (eg, colonoscopy, dental procedures) or limited accidental injury (eg, ankle sprains, minor fractures, minor burns/sunburns). Subjects should be counseled to avoid scheduling prospective procedures such that pain medications would be needed within 48 hours of a study visit. Contact the assigned study monitor or study clinician for guidance/approval regarding the use of prohibited medications for other self-limiting conditions, accidental injury or other surgical procedures as the extent of the condition, injury or procedure and the resulting pain medication usage may require termination from the study.

For subjects who have discontinued investigational product, the investigator may prescribe standard of care treatment for subjects to take while completing the 24-week Safety Follow-up period once the last efficacy assessments have been obtained at the visit occurring 16 weeks after the last dose of SC investigational product. In this study, standard of care treatment refers to analgesics approved by FDA (for US subjects) or another applicable Health Authority (for non-US subjects) to relieve the pain of osteoarthritis. These medications include opioids, topical analgesics, NSAIDs, capsaicin products, injectable corticosteroids and viscosupplementation (eg, hyaluronan) and are prescribed at the discretion of the Investigator. Pre-specified analgesics are not considered investigational product but will be reimbursed by Pfizer, if allowed per local regulation while the subject is participating in the 24-week Safety Follow-up period after at least 16 weeks have elapsed since their last dose of SC treatment was administered. Their use will be recorded on the concomitant medication CRF.

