## 6.4. Subject Withdrawal/Early Termination

Subjects may withdraw from the study at any time at their own request, or they may be withdrawn at any time at the discretion of the investigator or sponsor for safety or behavioral reasons, or the inability of the subject to comply with the protocol required schedule of study visits or procedures at a given study site.

If a subject does not return for a scheduled visit, every effort should be made to contact the subject. A subject thought to be lost to follow-up, must be contacted through a minimum of 3 documented phone call attempts and, if phone calls are unsuccessful, a certified letter sent to the subject. In any circumstance, every effort should be made to document the subject's outcome, if possible. The Investigator should inquire about the reason for withdrawal, request the return of all unused investigational product, follow-up with the subject regarding any unresolved adverse events and request that the subject return for follow-up visits as indicated in the schedule below. Females of child-bearing potential should be reminded to continue contraceptive measures at least 112 days (16 weeks) after the last dose of SC investigational product.

If the subject withdraws from the study, and also withdraws consent for disclosure of future information, no further evaluations should be performed, and no additional data should be collected. Pfizer may retain and continue to use any data collected before such withdrawal of consent.

Subjects discontinuing from treatment (prior to Week 56), whether at their request or at the decision of the investigator, will be required to undergo 24 weeks of post-treatment follow-up (as described in Section 6.4.1). The 24 weeks of follow-up will be obtained through 3 clinic visits and monthly phone calls to yield 24 weeks of follow-up, as described in Section 6.4.1. Subjects will be asked to continue to enter pain scores for index and non-index joints (as applicable) via IRT, weekly, through the end of the 24 week safety follow-up period. On a weekly basis during the 24 week safety follow-up period, subjects will also be asked to continue to record rescue medication and NSAID use.

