19. Summary of Dual Energy X-Ray Absorptiometry (DEXA) at screening, showing summary measures of bone mineral density, and t-scores of the spine and hip.
20. Summary of the Survey of Autonomic Symptoms (SAS) number of symptoms reported and total symptom impact score, at each visit, and for the change from Baseline score.
21. Summary of concomitant medications for Osteoarthritis for non-NSAID and NSAID medications (shown separately).
22. Summary of number of days of non-study NSAID use per dosing interval (eg, Day 1 to Week 8, Week 8 to Week 16, etc.) and for the first 8-week interval in the safety follow-up period. This will show the number and percentage of subjects in an interval who exceeded the limit of 10 days of NSAID use. If an interval exists, the visits will be used to define the interval, otherwise calendar time will be used. A summary of average number of days of NSAID use will be displayed by interval. Also, a summary of the overall number of days of NSAID use from Day 1 to Week 64 will be shown, as well as the number and percentage of subjects who exceeded the limit of 80 days of NSAID use during this interval.

09001776e1931781b656\Approved\Approved On: 08-10-2019 08:56 (GMT)

23. Summary of oral study medication compliance. This is calculated for the interval from Baseline to Week 16 and the entire post-Baseline period up to Week 56 (or end of treatment visit). Compliance is calculated as number of tablets dispensed minus the number returned divided by the number of days in the interval, all divided by 2 (for the daily regimen frequency), multiplied by 100, to get a percentage compliance for each subject for each time period.

Neurological-related safety data

The “conclusion from the neurological examination” data will be summarized for each time point and the last subject assessment. In addition the persistence of any neurological examination finding will be summarized, showing the incidence of subjects with new or worsened neurological examination abnormalities (both clinically significant only and also for any finding) for 2, 3, 4, and ≥ 5 consecutive visits.

Immunogenicity

The following assessments of ADA data will be made:

- A listing of individual serum ADA results sorted by treatment group, subject ID and planned visit. The listing will also include the actual test date/times.

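### The overall non-study NSAID total in SAP item 22 counts permitted standard-of-care days in early stoppers, and its fixed 80-day limit fits only subjects last dosed at Week 48 (minor)

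*SAP*

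**What the plan says.** Item 22 in SAP Section 8.2.3.2 has two parts.

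- **By interval.** Non-study NSAID days are summarised for each SC dosing interval "and for the first 8-week interval in the safety follow-up period". For each interval: "This will show the number and percentage of subjects in an interval who exceeded the limit of 10 days of NSAID use". On boundaries: "If an interval exists, the visits will be used to define the interval, otherwise calendar time will be used".
- **Overall.** "Also, a summary of the overall number of days of NSAID use from Day 1 to Week 64 will be shown". The same line also reports how many subjects, and what percentage, went above what the SAP calls a limit of 80 days. No earlier end date is given for subjects who stop treatment, and the limit is not scaled to time observed.

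The protocol supplies the background.

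- Section 5.8.1 prohibits non-study NSAIDs through the Week 64 visit. Its tolerance is set per 8-week SC dosing interval; action follows on "greater than 10 days (aggregate total) of concomitant NSAID use" with further use after counselling.
- Under Sections 5.8.2, 5.9 and 6.4, a subject who stops early may start standard of care after the visit about 16 weeks after the last SC dose, for the remaining 8 weeks of follow-up. On what that covers: "These medications include opioids, topical analgesics, NSAIDs, capsaicin products, injectable corticosteroids and viscosupplementation".
- Recording goes on throughout. Section 6.4 says that weekly during this follow-up "subjects will also be asked to continue to record rescue medication and NSAID use", and Section 7.1.3 confirms that over-the-counter and prescription NSAID days are collected weekly in early-termination follow-up.

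**The concern.** The overall line is presented as use against a limit, so a reader will take it as evidence on whether the NSAID restriction held. For anyone who stops early, the restriction ends well before calendar Week 64, but the count does not. Days that the protocol allows are then added to days that it forbids. The same subject is also judged against an allowance built up over 64 weeks of restriction that he or she never had.

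Early stopping is built into the design. The Week 16 response check is made before dosing (Protocol Section 6.2.6.1), so a subject who fails it was last dosed at Week 8. Because that check depends on pain response, the share of early stoppers can differ by arm.

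The table has a purpose: excluding chronic concomitant NSAID use is the first risk-minimisation measure listed in Protocol Section 1.2.3.4. The total and the percentage over the limit should therefore describe restricted time only.

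**Working it through.** **Inputs.** Tolerance of 10 days per 8-week interval (SAP item 22; Protocol 5.8.1). SC doses at Baseline and Weeks 8, 16, 24, 32, 40 and 48. Standard of care possible from 16 weeks after the last SC dose, with follow-up ending at 24 weeks (Protocol 5.9 and 6.4). Count window to Week 64. Nominal visit timing throughout.

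**Reproducing the 80 days.** Seven dosing intervals to Week 56, plus the first follow-up interval (Weeks 56 to 64), make 8. 8 × 10 = 80. The SAP does not state this derivation, but it fits exactly.

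**By week of last SC dose, L:**

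- restricted days = 7 × (L + 16)
- restricted intervals k = (L + 16)/8, so scaled limit = 10k
- permitted days inside the count = 7 × [min(L + 24, 64) − (L + 16)]
- highest total while keeping to 10 days per restricted interval = 10k + permitted days
- share of restricted days needed to exceed 80 = 81 / restricted days

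| L | Restricted days | k | Scaled limit | 80 ÷ scaled limit | Share needed to exceed 80 | Permitted days counted | Highest compliant total |
|---|---|---|---|---|---|---|---|
| 0 | 112 | 2 | 20 | 4.00 | 72% | 56 | 76 |
| 8 | 168 | 3 | 30 | 2.67 | 48% | 56 | 86 |
| 16 | 224 | 4 | 40 | 2.00 | 36% | 56 | 96 |
| 24 | 280 | 5 | 50 | 1.60 | 29% | 56 | 106 |
| 32 | 336 | 6 | 60 | 1.33 | 24% | 56 | 116 |
| 40 | 392 | 7 | 70 | 1.14 | 21% | 56 | 126 |
| 48 | 448 | 8 | 80 | 1.00 | 18% | 0 | 80 |

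**False flags.** Permitted days alone cannot exceed 80, because their maximum is 56. With all 56 used, 81 − 56 = 25 earlier days are enough. A subject last dosed at Week 8 with 25 to 30 days over three restricted intervals could have kept within 10 per interval and still be counted as over the limit. With a last dose at Baseline the highest compliant total is 76, so no such flag arises.

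**Leniency.** A subject last dosed at Week 8 can have 31 to 80 days in restricted time without passing the overall limit, although the scaled limit is 30. Exceeding 80 is impossible only for someone observed for 80 days or fewer. For other early stoppers it is possible but needs much heavier use than in a completer (18%).

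**What the interval table catches.** If every one of k intervals has at most 10 days, the total is at most 10k. So anyone above 10k days has more than 10 in at least one interval and appears in the per-interval counts. For example, 31 days over three intervals cannot be split without one exceeding 10.

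**The case against.** The strongest reply is that item 22 already contains the right table. The per-interval summary does not depend on length of follow-up. If its first follow-up interval is taken as weeks 8 to 16 after the last dose, it also ends where standard of care may begin. By the argument above, a scaled overall limit would identify nobody whom that table misses. This stands in full. A reader might infer from the fixed 80 days that over-use in early stoppers goes undetected; the documents do not support that. Only the overall line is lenient.

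A second reply is that Week 64 may have been meant as the visit 16 weeks after the last dose, since Protocol Section 5.9 describes it in those words. On that reading the permitted days drop out. It is possible, but item 22 does not say it, and its fallback for missing intervals is calendar time. SAP Appendix 1.1 also defines Week 64 by study day (target 449) and sets up a separate window for 16 weeks after the last dose, so elsewhere the SAP treats the two as different. Even on this reading, the fixed 80 would still not match the shorter restricted period.

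Third, a fixed cumulative total can be a legitimate description, and the protocol has no 80-day rule. That has some force, but the SAP calls 80 a limit and reports the percentage exceeding it, which invites a compliance reading.

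Finally, the table is descriptive. No endpoint, significance level or stopping rule depends on it, and compliance is managed during the study under Protocol Section 5.8.1. This also stands and sets the severity.

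**Conclusion.** The point holds as a minor correction. Read literally, the overall total includes up to 56 permitted days for every last-dose week from Baseline to Week 40. A compliant subject can be counted as over the limit at 86 to 126 days for last doses at Weeks 8 to 40. The 80-day limit matches only a last dose at Week 48 and is 1.14 to 4 times the scaled limit otherwise.

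This rests on nominal timing, on calendar Week 64, and on standard-of-care NSAID days being entered in the weekly record. Protocol Section 7.1.3 supports the last of these, although the SAP does not name its data source. The 56 days is a ceiling: standard of care is given as needed and includes several non-NSAID options.

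Two larger readings are tempting and should not be drawn. One is that the arms are biased by a known amount; the documents give neither stopping rates by arm nor standard-of-care NSAID use, so no such size can be stated. The other is that the 1.8% versus 0.5% joint-event contrast in Protocol Table 3 measures what is at stake here. That table compares tanezumab plus NSAID with monotherapy at 2.5 to 10 mg before risk mitigation. It does not address NSAID use 16 weeks or more after the last dose.

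**What to change.** In the overall part of item 22:

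- count non-study NSAID days from Day 1 to the earlier of Week 64 and 16 weeks after the last SC dose;
- replace the fixed 80-day flag with 10 days per 8-week interval observed, or show days per 8 recorded weeks.

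The first change leaves completers dosed through Week 48 as they are. The second gives limits of 20, 30, 40, 50, 60, 70 and 80 days for last doses at Baseline to Week 48. The per-interval part can stay. Anchoring to the last SC dose follows what SAP Section 8 and Appendix 1.1 already do for efficacy data.

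The cost is SAP wording and programming, because dosing dates and weekly entries are already collected. The change concerns only how use is reported. The protocol's rules on NSAID use and withdrawal are untouched.

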8.2.4. Other Analyses

8.2.4.1. Pharmacokinetics

The following reporting of PK data will be done:

- A listing of all plasma tanezumab concentrations sorted by subject, active treatment group and nominal time post dose. The listing of concentrations will also include the actual times post dose.
- A descriptive summary of the plasma tanezumab concentrations based on nominal time post dose for each treatment group.
- Boxplots of plasma tanezumab concentrations at the nominal times for the tanezumab treatment groups.

09001776e1931781b656\Approved\Approved On: 08-10-2019 08:56 (GMT)

- A listing of available synovial fluid tanezumab concentrations at the time of the arthrocentesis only sorted by subject, treatment group and actual collection date and time.

8.2.4.2. Pharmacodynamics (NGF)

Serum samples from a subset of patients will be run in the bioanalytical assays for assessment of NGF and the measurements will be summarized in the following tables and figures.

- A listing of individual serum NGF concentrations sorted by subject, treatment group and time post dose.
- Descriptive statistics of serum NGF concentrations based on time post dose for each treatment group.
- Boxplots of serum NGF over time post dose for each treatment group.

If enough synovial fluid volume is left after determining the tanezumab concentration in the sample that is collected in subjects who have arthrocentesis performed, synovial fluid NGF concentrations will be determined as well at the time of the arthrocentesis only, and the measurements will be summarized as follows:

- A listing of available synovial fluid NGF concentrations at the time of the arthrocentesis only sorted by subject, treatment group and actual collection date and time.

8.2.4.3. Osteoarthritis Biomarkers

The biomarker data analysis related to joint safety events will be performed separately from the A4091058 study CSR.

09001776e493181b6561ApprovedApproved On: 03-10-2019 08:56 (GMT)

8.2.5. Summary of Efficacy Analyses

Note: BL=Baseline

Endpoint	Analysis Set	Statistical Method	Model/Covariates	Missing Data	Objective
Change from Baseline to Week 16 in WOMAC Pain subscale	ITT	ANCOVA	BL Score, BL Diary Average Pain, Index Joint (Knee/Hip), Highest KL grade (2, 3 or 4), NSAID cohort, Treatment Group (Study site as a random effect)	Multiple Imputation	Primary Analysis
Change from Baseline to Week 16 in WOMAC Physical Function subscale	ITT	ANCOVA	BL Score, BL Diary Average Pain, Index Joint (Knee/Hip), Highest KL grade (2, 3 or 4), NSAID cohort, Treatment Group (Study site as a random effect)	Multiple Imputation	Primary Analysis
Change from Baseline to Week 16 in Patient Global Assessment of Osteoarthritis	ITT	ANCOVA	BL Score, BL Diary Average Pain, Index Joint (Knee/Hip), Highest KL grade (2, 3 or 4), NSAID cohort, Treatment Group (Study site as a random effect)	Multiple Imputation	Primary Analysis
Change from Baseline to Week 16 in WOMAC Pain subscale	ITT	ANCOVA	BL Score, BL Diary Average Pain, Index Joint (Knee/Hip), Highest KL grade (2, 3 or 4), NSAID cohort, Study Site, Treatment Group, Study Site x Treatment Group (Study site and interaction as random effects)	Multiple Imputation	Additional (Interaction) Analysis
Change from Baseline to Week 16 in WOMAC Pain subscale	ITT	ANCOVA	BL Score, BL Diary Average Pain, Index Joint (Knee/Hip), Highest KL grade (2, 3 or 4), NSAID cohort, Country, Treatment Group, Country x Treatment Group.	Multiple Imputation	Additional (Interaction) Analysis
Change from Baseline to Week 16 in WOMAC Physical Function subscale	ITT	ANCOVA	BL Score, BL Diary Average Pain, Index Joint (Knee/Hip), Highest KL grade (2, 3 or 4),	Multiple Imputation	Additional (Interaction) Analysis

09/01/2019 17:56:56 Approved On: 08/10/2019 08:56 (GMT)

09/01/17 11:33:18 AM Approved On: 08/10/2019 08:56 (GMT)

			NSAID cohort, Study Site, Treatment Group, Study Site x Treatment Group (Study site and interaction as random effects)		
Change from Baseline to Week 16 in WOMAC Physical Function subscale	ITT	ANCOVA	BL Score, BL Diary Average Pain, Index Joint (Knee/Hip), Highest KL grade (2, 3 or 4), NSAID cohort, Country, Treatment Group, Country x Treatment Group.	Multiple Imputation	Additional (Interaction) Analysis
Change from Baseline to Week 16 in Patient Global Assessment of Osteoarthritis	ITT	ANCOVA	BL Score, BL Diary Average Pain, Index Joint (Knee/Hip), Highest KL grade (2, 3 or 4), NSAID cohort, Study Site, Treatment Group, Study Site x Treatment Group (Study site and interaction as random effects)	Multiple Imputation	Additional (Interaction) Analysis
Change from Baseline to Week 16 in Patient Global Assessment of Osteoarthritis	ITT	ANCOVA	BL Score, BL Diary Average Pain, Index Joint (Knee/Hip), Highest KL grade (2, 3 or 4), NSAID cohort, Country, Treatment Group, Country x Treatment Group	Multiple Imputation	Additional (Interaction) Analysis
Change from Baseline to Week 16 in WOMAC Pain subscale	PP	ANCOVA	BL Score, BL Diary Average Pain, Index Joint (Knee/Hip), Highest KL grade (2, 3 or 4), NSAID cohort, Treatment Group (Study site as a random effect)	Multiple Imputation	Sensitivity Analysis (Per protocol)
Change from Baseline to Week 16 in WOMAC Physical Function subscale	PP	ANCOVA	BL Score, BL Diary Average Pain, Index Joint (Knee/Hip), Highest KL grade (2, 3 or 4), NSAID cohort, Treatment Group (Study site as a random effect)	Multiple Imputation	Sensitivity Analysis (Per protocol)
Change from Baseline to Week 16 in Patient Global Assessment of Osteoarthritis	PP	ANCOVA	BL Score, BL Diary Average Pain, Index Joint (Knee/Hip), Highest KL grade (2, 3 or 4), NSAID cohort, Treatment Group	Multiple Imputation	Sensitivity Analysis (Per protocol)

0900177e493181b0561Approved\Approved On: 08-10-2019 08:56 (GMT)

			(Study site as a random effect)		
Change from Baseline to Week 16 in WOMAC Pain subscale	ITT	ANCOVA	BL Score, BL Diary Average Pain, Index Joint (Knee/Hip), Highest KL grade (2, 3 or 4), NSAID cohort, Treatment Group (Study site as a random effect)	BOCF	Sensitivity Analysis
Change from Baseline to Week 16 in WOMAC Physical Function subscale	ITT	ANCOVA	BL Score, BL Diary Average Pain, Index Joint (Knee/Hip), Highest KL grade (2, 3 or 4), NSAID cohort, Treatment Group (Study site as a random effect)	BOCF	Sensitivity Analysis
Change from Baseline to Week 16 in Patient Global Assessment of Osteoarthritis	ITT	ANCOVA	BL Score, BL Diary Average Pain, Index Joint (Knee/Hip), Highest KL grade (2, 3 or 4), NSAID cohort, Treatment Group (Study site as a random effect)	BOCF	Sensitivity Analysis
Change from Baseline to Week 16 in WOMAC Pain subscale	ITT	ANCOVA	BL Score, BL Diary Average Pain, Index Joint (Knee/Hip), Highest KL grade (2, 3 or 4), NSAID cohort, Treatment Group (Study site as a random effect)	LOCF	Sensitivity Analysis
Change from Baseline to Week 16 in WOMAC Physical Function subscale	ITT	ANCOVA	BL Score, BL Diary Average Pain, Index Joint (Knee/Hip), Highest KL grade (2, 3 or 4), NSAID cohort, Treatment Group (Study site as a random effect)	LOCF	Sensitivity Analysis
Change from Baseline to Week 16 in Patient Global Assessment of Osteoarthritis	ITT	ANCOVA	BL Score, BL Diary Average Pain, Index Joint (Knee/Hip), Highest KL grade (2, 3 or 4), NSAID cohort, Treatment Group (Study site as a random effect)	LOCF	Sensitivity Analysis
Change from Baseline to Weeks 2, 4, 8 and 16 in WOMAC Pain subscale	ITT	MMRM	BL Score, BL Diary Average Pain, Index Joint (Knee/Hip), Highest KL grade (2, 3 or 4), NSAID cohort, Time, Treatment Group, Time x Treatment Group (Study site as a random effect)	Observed Data	Sensitivity Analysis for Week 16 (Secondary Endpoint Analysis for other time points)
Change from Baseline to Weeks 2, 4,	ITT	MMRM	BL Score, BL Diary Average	Observed Data	Sensitivity Analysis

8 and 16 in WOMAC Physical Function subscale			Pain, Index Joint (Knee/Hip), Highest KL grade (2, 3 or 4), NSAID cohort, Time, Treatment Group, Time x Treatment Group (Study site as a random effect)		for Week 16 (Secondary Endpoint Analysis for other time points)
Change from Baseline to Weeks 2, 4, 8 and 16 in Patient Global Assessment of Osteoarthritis	ITT	MMRM	BL Score, BL Diary Average Pain, Index Joint (Knee/Hip), Highest KL grade (2, 3 or 4), NSAID cohort, Time, Treatment Group, Time x Treatment Group (Study site as a random effect)	Observed Data	Sensitivity Analysis for Week 16 (Secondary Endpoint Analysis for other time points)
Change from Baseline to Weeks 2, 4, 8, 16, 24, 32, 40, 48, and 56 in Patient Global Assessment of Osteoarthritis	ITT	CMH test	Treatment Group [1]	Mixed BOCF/LOCF	Sensitivity Analysis for PGA
Change from Baseline to Week 16 in WOMAC Pain subscale, shown by site (sites with n≥30)	ITT	None (summary)	NA	Multiple Imputation	Supportive summary for interaction analysis
Change from Baseline to Week 16 in WOMAC Physical Function subscale, shown by site (sites with n≥30)	ITT	None (summary)	NA	Multiple Imputation	Supportive summary for interaction analysis
Change from Baseline to Week 16 in Patient Global Assessment of Osteoarthritis, shown by site (sites with n≥30)	ITT	None (summary)	NA	Multiple Imputation	Supportive summary for interaction analysis
Change from Baseline to Week 16 in WOMAC Pain subscale, shown by country (countries with n≥30)	ITT	None (summary)	NA	Multiple Imputation	Supportive summary for interaction analysis
Change from Baseline to Week 16 in WOMAC Physical Function subscale, shown by country (countries with n≥30)	ITT	None (summary)	NA	Multiple Imputation	Supportive summary for interaction analysis
Change from Baseline to Week 16 in Patient Global Assessment of Osteoarthritis, shown by country (countries with n≥30)	ITT	None (summary)	NA	Multiple Imputation	Supportive summary for interaction analysis
Missing data pattern for WOMAC Pain subscale for Baseline and Weeks 2, 4, 8 and 16	ITT	None (summary)	NA	Observed Data	Supportive summary for missing data

0900177e493181b050Approved\Approved On: 08-10-2019 08:56 (GMT)

09/01/2019 17:56:56 Approved On: 08/10/2019 08:56 (GMT)

Missing data pattern for WOMAC Physical Function subscale for Baseline and Weeks 2, 4, 8 and 16	ITT	None (summary)	NA	Observed Data	Supportive summary for missing data
Missing data pattern for Patient Global Assessment of Osteoarthritis for Baseline and Weeks 2, 4, 8 and 16	ITT	None (summary)	NA	Observed Data	Supportive summary for missing data
Change from Baseline to Week 16 in WOMAC Pain subscale by NSAID cohort	ITT	ANCOVA	BL Score, BL Diary Average Pain, Index Joint (Knee/Hip), Highest KL grade (2, 3 or 4), Treatment Group (Study site as a random effect)	Multiple Imputation	Primary endpoint analysis for individual NSAID comparisons
Change from Baseline to Week 16 in WOMAC Physical Function subscale by NSAID cohort	ITT	ANCOVA	BL Score, BL Diary Average Pain, Index Joint (Knee/Hip), Highest KL grade (2, 3 or 4), Treatment Group (Study site as a random effect)	Multiple Imputation	Primary endpoint analysis for individual NSAID comparisons
Change from Baseline to Week 16 in Patient Global Assessment of Osteoarthritis by NSAID cohort	ITT	ANCOVA	BL Score, BL Diary Average Pain, Index Joint (Knee/Hip), Highest KL grade (2, 3 or 4), Treatment Group (Study site as a random effect)	Multiple Imputation	Primary endpoint analysis for individual NSAID comparisons
Change from Baseline to Weeks 2, 4, 8, 24, 32, 40, 48, and 56 in WOMAC Pain subscale	ITT	ANCOVA	BL Score, BL Diary Average Pain, Index Joint (Knee/Hip), Highest KL grade (2, 3 or 4), NSAID cohort, Treatment Group (Study site as a random effect)	Multiple Imputation	Secondary Endpoint Analysis
Change from Baseline to Weeks 2, 4, 8, 24, 32, 40, 48, and 56 in WOMAC Pain subscale	ITT	ANCOVA	BL Score, BL Diary Average Pain, Index Joint (Knee/Hip), Highest KL grade (2, 3 or 4), NSAID cohort, Treatment Group (Study site as a random effect)	BOCF	Secondary Endpoint Analysis
Change from Baseline to Weeks 2, 4, 8, 24, 32, 40, 48, and 56 in WOMAC Pain subscale	ITT	ANCOVA	BL Score, BL Diary Average Pain, Index Joint (Knee/Hip), Highest KL grade (2, 3 or 4), NSAID cohort, Treatment Group (Study site as a random effect)	LOCF	Secondary Endpoint Analysis

09001776e193781b0561Approved\Approved On: 08-10-2019 08:56 (GMT)

Change from Baseline to Weeks 2, 4, 8, 24, 32, 40, 48, and 56 in WOMAC Physical Function subscale	ITT	ANCOVA	BL Score, BL Diary Average Pain, Index Joint (Knee/Hip), Highest KL grade (2, 3 or 4), NSAID cohort, Treatment Group (Study site as a random effect)	Multiple Imputation	Secondary Endpoint Analysis
Change from Baseline to Weeks 2, 4, 8, 24, 32, 40, 48, and 56 in WOMAC Physical Function subscale	ITT	ANCOVA	BL Score, BL Diary Average Pain, Index Joint (Knee/Hip), Highest KL grade (2, 3 or 4), NSAID cohort, Treatment Group (Study site as a random effect)	BOCF	Secondary Endpoint Analysis
Change from Baseline to Weeks 2, 4, 8, 24, 32, 40, 48, and 56 in WOMAC Physical Function subscale	ITT	ANCOVA	BL Score, BL Diary Average Pain, Index Joint (Knee/Hip), Highest KL grade (2, 3 or 4), NSAID cohort, Treatment Group (Study site as a random effect)	LOCF	Secondary Endpoint Analysis
Change from Baseline to Weeks 2, 4, 8, 24, 32, 40, 48, and 56 in Patient Global Assessment of Osteoarthritis	ITT	ANCOVA	BL Score, BL Diary Average Pain, Index Joint (Knee/Hip), Highest KL grade (2, 3 or 4), NSAID cohort, Treatment Group (Study site as a random effect)	Multiple Imputation	Secondary Endpoint Analysis
Change from Baseline to Weeks 2, 4, 8, 24, 32, 40, 48, and 56 in Patient Global Assessment of Osteoarthritis	ITT	ANCOVA	BL Score, BL Diary Average Pain, Index Joint (Knee/Hip), Highest KL grade (2, 3 or 4), NSAID cohort, Treatment Group (Study site as a random effect)	BOCF	Secondary Endpoint Analysis
Change from Baseline to Weeks 2, 4, 8, 24, 32, 40, 48, and 56 in Patient Global Assessment of Osteoarthritis	ITT	ANCOVA	BL Score, BL Diary Average Pain, Index Joint (Knee/Hip), Highest KL grade (2, 3 or 4), NSAID cohort, Treatment Group (Study site as a random effect)	LOCF	Secondary Endpoint Analysis
The OMERACT-OARSI response at Weeks 2, 4, 8, 16, 24, 32, 40, 48, and 56	ITT	Logistic Regression	BL Score (WOMAC Pain), BL Diary Average Pain, Index Joint (Knee/Hip), Highest KL grade (2, 3 or 4), NSAID cohort, Treatment Group	Mixed BOCF/LOCF	Secondary Endpoint Analysis

0900177ed19378b056ApprovedApproved On: 08-10-2019 08:56 (GMT)

The OMERACT-OARSI response at Weeks 2, 4, 8, 16, 24, 32, 40, 48, and 56	ITT	Logistic Regression	BL Score (WOMAC Pain), BL Diary Average Pain, Index Joint (Knee/Hip), Highest KL grade (2, 3 or 4), NSAID cohort, Treatment Group	BOCF	Secondary Endpoint Analysis
The OMERACT-OARSI response at Weeks 2, 4, 8, 16, 24, 32, 40, 48, and 56	ITT	Logistic Regression	BL Score (WOMAC Pain), BL Diary Average Pain, Index Joint (Knee/Hip), Highest KL grade (2, 3 or 4), NSAID cohort, Treatment Group	LOCF	Secondary Endpoint Analysis
Percentage of subjects with reduction of $\geq 30/50/70/90\%$ from Baseline to Weeks 2, 4, 8, 16, 24, 32, 40, 48, and 56 in the WOMAC Pain subscale	ITT	Logistic Regression	BL Score, BL Diary Average Pain, Index Joint (Knee/Hip), Highest KL grade (2, 3 or 4), NSAID cohort, Treatment Group	Mixed BOCF/LOCF	Secondary Endpoint Analysis
Percentage of subjects with reduction of $\geq 30/50/70/90\%$ from Baseline to Weeks 2, 4, 8, 16, 24, 32, 40, 48, and 56 in the WOMAC Pain subscale	ITT	Logistic Regression	BL Score, BL Diary Average Pain, Index Joint (Knee/Hip), Highest KL grade (2, 3 or 4), NSAID cohort, Treatment Group	BOCF	Secondary Endpoint Analysis
Percentage of subjects with reduction of $\geq 30/50/70/90\%$ from Baseline to Weeks 2, 4, 8, 16, 24, 32, 40, 48, and 56 in the WOMAC Pain subscale	ITT	Logistic Regression	BL Score, BL Diary Average Pain, Index Joint (Knee/Hip), Highest KL grade (2, 3 or 4), NSAID cohort, Treatment Group	LOCF	Secondary Endpoint Analysis
Percentage of subjects with reduction of $\geq 30/50/70/90\%$ from Baseline to Weeks 2, 4, 8, 16, 24, 32, 40, 48, and 56 in the WOMAC Physical Functioning subscale	ITT	Logistic Regression	BL Score, BL Diary Average Pain, Index Joint (Knee/Hip), Highest KL grade (2, 3 or 4), NSAID cohort, Treatment Group	Mixed BOCF/LOCF	Secondary Endpoint Analysis
Percentage of subjects with reduction of $\geq 30/50/70/90\%$ from Baseline to Weeks 2, 4, 8, 16, 24, 32, 40, 48, and 56 in the WOMAC Physical Functioning subscale	ITT	Logistic Regression	BL Score, BL Diary Average Pain, Index Joint (Knee/Hip), Highest KL grade (2, 3 or 4), NSAID cohort, Treatment Group	BOCF	Secondary Endpoint Analysis
Percentage of subjects with reduction of $\geq 30/50/70/90\%$ from Baseline to Weeks 2, 4, 8, 16, 24, 32, 40, 48, and 56 in the WOMAC Physical Functioning subscale	ITT	Logistic Regression	BL Score, BL Diary Average Pain, Index Joint (Knee/Hip), Highest KL grade (2, 3 or 4), NSAID cohort, Treatment Group	LOCF	Secondary Endpoint Analysis

09001776e193181b0561Approved\Approved On: 08-10-2019 08:56 (GMT)

Percentage of subjects with an improvement of ≥ 2 points from Baseline to Weeks 2, 4, 8, 16, 24, 32, 40, 48, and 56 in the Patient Global Assessment of Osteoarthritis	ITT	Logistic Regression	BL Score, BL Diary Average Pain, Index Joint (Knee/Hip), Highest KL grade (2, 3 or 4), NSAID cohort, Treatment Group	Mixed BOCF/LOCF	Secondary Endpoint Analysis
Percentage of subjects with an improvement of ≥ 2 points from Baseline to Weeks 2, 4, 8, 16, 24, 32, 40, 48, and 56 in the Patient Global Assessment of Osteoarthritis	ITT	Logistic Regression	BL Score, BL Diary Average Pain, Index Joint (Knee/Hip), Highest KL grade (2, 3 or 4), NSAID cohort, Treatment Group	BOCF	Secondary Endpoint Analysis
Percentage of subjects with an improvement of ≥ 2 points from Baseline to Weeks 2, 4, 8, 16, 24, 32, 40, 48, and 56 in the Patient Global Assessment of Osteoarthritis	ITT	Logistic Regression	BL Score, BL Diary Average Pain, Index Joint (Knee/Hip), Highest KL grade (2, 3 or 4), NSAID cohort, Treatment Group	LOCF	Secondary Endpoint Analysis
Reduction of $>0\%$, $\geq 10\%$, to $\geq 90\%$ (in steps of 10%) and $=100\%$ from Baseline to Week 16, 24 and 56 in the WOMAC Pain subscale	ITT	None (summary and plot)	NA	Mixed BOCF/LOCF	Secondary Endpoint Analysis
Reduction of $>0\%$, $\geq 10\%$, to $\geq 90\%$ (in steps of 10%) and $=100\%$ from Baseline to Week 16, 24 and 56 in the WOMAC Pain subscale	ITT	None (summary)	NA	BOCF	Secondary Endpoint Analysis
Reduction of $>0\%$, $\geq 10\%$, to $\geq 90\%$ (in steps of 10%) and $=100\%$ from Baseline to Week 16, 24 and 56 in the WOMAC Pain subscale	ITT	None (summary)	NA	LOCF	Secondary Endpoint Analysis
Reduction of $>0\%$, $\geq 10\%$, to $\geq 90\%$ (in steps of 10%) and $=100\%$ from Baseline to Week 16, 24 and 56 in the WOMAC Physical Function subscale	ITT	None (summary and plot)	NA	Mixed BOCF/LOCF	Secondary Endpoint Analysis
Reduction of $>0\%$, $\geq 10\%$, to $\geq 90\%$ (in steps of 10%) and $=100\%$ from Baseline to Week 16, 24 and 56 in the WOMAC Physical Function subscale	ITT	None (summary)	NA	BOCF	Secondary Endpoint Analysis

0900177 (e193181b056) Approved/Approved On: 08-10-2019 08:56 (GMT)

Reduction of >0%, ≥10%, to ≥90% (in steps of 10%) and =100% from Baseline to Week 16, 24 and 56 in the WOMAC Physical Function subscale	ITT	None (summary)	NA	LOCF	Secondary Endpoint Analysis
Change from Baseline to Weeks 2, 4, 8, 16, 24, 32, 40, 48, and 56 in the WOMAC Stiffness subscale	ITT	ANCOVA	BL Score, BL Diary Average Pain, Index Joint (Knee/Hip), Highest KL grade (2, 3 or 4), NSAID cohort, Treatment Group (Study site as a random effect)	Multiple Imputation	Secondary Endpoint Analysis
Change from Baseline to Weeks 2, 4, 8, 16, 24, 32, 40, 48, and 56 in the WOMAC Average Score	ITT	ANCOVA	BL Score, BL Diary Average Pain, Index Joint (Knee/Hip), Highest KL grade (2, 3 or 4), NSAID cohort, Treatment Group (Study site as a random effect)	Multiple Imputation	Secondary Endpoint Analysis
Change from Baseline to Weeks 2, 4, 8, 16, 24, 32, 40, 48, and 56 in the WOMAC Item: Pain When Walking on a Flat Surface	ITT	ANCOVA	BL Score, BL Diary Average Pain, Index Joint (Knee/Hip), Highest KL grade (2, 3 or 4), NSAID cohort, Treatment Group (Study site as a random effect)	Multiple Imputation	Secondary Endpoint Analysis
Change from Baseline to Weeks 2, 4, 8, 16, 24, 32, 40, 48, and 56 in the WOMAC Item: Pain When Going Up or Down Stairs	ITT	ANCOVA	BL Score, BL Diary Average Pain, Index Joint (Knee/Hip), Highest KL grade (2, 3 or 4), NSAID cohort, Treatment Group (Study site as a random effect)	Multiple Imputation	Secondary Endpoint Analysis
Change from Baseline to Days 1, 2, 3, 4, 5, 6, 7, and to Weeks 1, 2, 3, 4, 6, 8, 10, 12, 16, 20, 24, 32, 40, 48, and 56 in the weekly average pain score in the index joint	ITT	ANCOVA	BL Score, Index Joint (Knee/Hip), Highest KL grade (2, 3 or 4), NSAID cohort, Treatment Group (Study site as a random effect)	Multiple Imputation	Secondary Endpoint Analysis
Time to treatment discontinuation due to lack of efficacy (up to Week 56/End of Treatment)	ITT	Log-Rank (with KM estimates)	Treatment Group	Observed	Secondary Endpoint Analysis
